11.3. Termination and interruption criteria

- **Study termination criteria.** Completion of the 30-day follow-up period of the last patient included in the study.
- **Patient completion criteria.** Completion of the follow-up 30 days after the intervention.
- **Patient discontinuation criteria.** At least one of the following must be met:
 - Serious adverse events related to drug administration.
 - Development of contraindications or study exclusion criteria within the inclusion period and prior to surgery.
 - Voluntary drop-out of previously included patients.

12. Informed Consent (IC) and Patient Information Sheet (PIS)

The investigator will explain to each patient (witness or legal representative) the nature of the study/trial and the purposes, procedures, estimated duration, possible risks and benefits of their participation in the study/trial and possible inconveniences that this may cause them. All patients will be informed of the voluntary nature of their participation and that they may withdraw at any time, without affecting their future medical care or their relationship with the physician responsible for their treatment.

The patient shall be given sufficient time to read and understand the explanations included in the patient information sheet before giving informed consent (Annex 3). No patient shall be included in the study/trial before informed consent has been obtained.

Each patient will be assigned to an intervention group which will involve the administration of a dose at a predetermined time. All patients will receive the study product as there is no placebo group. The reason for the existence of 4 comparative groups is to study the efficacy of different dosage and interval of administration of the IV. Participation in the study

does not involve a different surgical procedure or an increase in the number of scheduled visits.

13. Data Collection Notebook -CRD-

The data collected will be recorded in a CRD, the veracity of which will be validated by the designated monitors. Each patient will be identified in the CRD by means of an alphanumeric code that identifies the patient (and the centre if it is a Multicentre) and in correlative order. The data protection provisions of Organic Law 3/2018 on Personal Data Protection and guarantee of digital rights will be respected at all times.

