20.12. Report to researchers

The sponsor will submit safety information that could impact the safety of the patients enrolled in the trial to the investigators as early as possible. In addition, the investigator will be informed throughout the study of any safety issues, including protocol modifications due to safety concerns.

21. Statistics

For the calculation of the sample size we estimated an average annual number of laparoscopic cholecystectomies of 300 cases. Assuming a minimum recruitment rate of 50% in the study, a duration of 12 months and possible losses of patients, we estimate a sample size of 200 patients.

Since the main objective is to analyse whether there are differences between the doses and administration times of the 4 treatment groups in which categorical variables will be measured, the effect of the chosen sample size ($n=200$) on the statistical contrasts in this type of variables is $w=0.25$ with a power.95 and a significance error of the null hypothesis $\alpha=0.05$.

The procedure used to account for missing, unused and erroneous data will be the "*Pairwise Delection*" method. The confidence intervals of the statistics will be 95% and the contrasts will be performed at a significance level of 5%. All analyses will be performed with the free software R (version 4.1.2+, R Core Team, Vienna, <https://www.R-project.org/>) and the RStudio interface (version 1.4.1103+).

The study will have no planned intermediate analyses as no partial analysis of results is envisaged. Once all data have been collected, verified and validated, a statistical analysis of the data will be performed according to the specifications described in the protocol. If this analysis leads to the conclusion that further analysis is necessary, this will be reported in the final analysis of results. All treated and evaluable subjects shall be analysed. Different statistical tools will be used depending on the nature of the variables collected in the study, accompanying the results with their corresponding graphs.

Lilliefors-Kolmogorov-Smirnov and Shapiro-Wilks tests shall be performed to study the normality of the distribution of quantitative variables, and to their distribution they shall be represented by the mean (standard deviation) or the median (median deviation) and may be accompanied by their corresponding confidence intervals. The relationship between such variables shall be measured with Pearson's or Spearman's correlation coefficients.

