The distributions of the categorical variables will be studied by means of frequencies and percentages. To represent and measure the dependence between them, contingency tables will be used with Pearson's Chi-square test, Fisher's exact test, McNemar's test

or Cochran's Q. A category comparison study could also be done using odds ratios between categories of clinical interest. To study the influence that some categorical variables might have on quantitative variables, ANOVA tests could be performed.

Finally, all the statistical information obtained on the relevance of each variable in the study could be used to apply classification tools to the individuals in the study (decision trees, logistic regression, ROC curves).

22. Direct Access to Source Data/Documents

The Promoter will enter into appropriate arrangements to appoint a monitor to oversee this study and to liaise regularly with the site, including arranging site visits. The investigator agrees to allow the monitor direct access to all relevant documents and to give his/her time and that of his/her staff to the monitor to discuss the results and any issues of concern.

23. Quality Control and Quality Assurance

In order to ensure the quality of the data, the promoter:

- Provide quality instruction and training to the research staff prior to the start of the study. Training topics include, but are not limited to: Good Clinical Practice (GCP) certificates, Adverse Event (AE) reporting, study details and procedures, study documentation, informed consent, and patient recruitment.

- Conduct regular monitoring in accordance with the International Conference on Harmonisation (ICH) for Good Clinical Practice (GCP). Data will be assessed for compliance with the protocol and for accuracy in relation to the source documents. Monitors will verify that the clinical trial is conducted, that data are generated, documented and reported in compliance with the protocol, good clinical practice and any applicable local regulatory requirements.

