DOTIG CLINICAL TRIAL (NCT05419947) STATISTICAL ANALYSIS

Study promoter	Castilla y Institute of Health Sciences Studies Foundation (IECSCYL)- Institute of Biomedical Research of Salamanca (IBSAL)	
EUDRA CT number	2022-000904-36	
Promoter's Protocol Code	IBS-DOTIG-ECM-2202	
Title	Randomised clinical trial to evaluate the dose and time of administration of indocyanine green in near-infrared fluorescein cholangiography during laparoscopic cholecystectomy.	
Date	16/12/2022	

1. Working hypothesis. There are differences in the visualisation rates of extrahepatic biliary structures as a function of drug dose and time of administration.

To test the hypothesis, we created four intervention groups combining two doses (fixed dose of 2.5 mg and weight-adjusted dose ratio of 0.05 mg/kg body weight) and two administration times (15-30 minutes preoperatively and >3 hours preoperatively). The primary endpoints are dichotomous and polytomous qualitative variables.

Before analysing the main and secondary objectives, the groups (G1, G2, G3, G4) and their baseline characteristics should be compared in order to demonstrate that they are homogeneous and the randomisation has been correct. To do this, the following variables collected in the CRDe should be compared:

- Sex (male/female)
- Age (years)
- BMI (kg/m2)
- ASA classification (ASA I/II/III/IV/IV/V)
- Previous abdominal surgeries (NO/SI). In the YES group, break down the variables biliary/liver/pancreas/intestinal/other).
- Previous liver disease (NO/SI). In the SI group, break down the variables: fatty liver disease, hepatitis, liver cirrhosis.
- Previous biliary examinations (NO/SI). In the SI group, break down the ERCP/CTPH variables.
- Previous biliary prostheses (NO/YES)
- Previous acute cholecystitis (NO/SI).
- Previous acute cholangitis (NO/SI).

- Previous gallbladder drainage (NO/SI). In the SI group, break down the variables percutaneous cholecystostomy/endoscopic cholecystostomy.
- Indication for surgery (biliary colic/acute cholecystitis/choledocholithiasis/acute cholangitis/acute lithiasic pancreatitis/bladder polyps/bladder adenomyomatosis).
- Type of surgery (elective/early/deferred surgery). Probably in this variable we do not have a very similar N, because most of them, at least in our centre, were elective.
- Grade of cholecystitis (1/2/3). In case of early indication/delayed urgency.
- Imaging system (Olympus/Karl-Storz/Stryker)
- Type of optics (30 degrees/ 0 degrees).

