- 2. Main objective. To analyse whether there are differences between different doses (single dose and weight-adjusted dose) and different VI administration intervals in the visualisation rates of extrahepatic biliary structures.

Carry out a comparative analysis between the different groups (G1/G2/G3/G4) and the following qualitative variables:

- Identification of biliary structures prior to dissection of the hepatocystic triangle.

o Identification of cystic duct (yes/no).

o Identification of common bile duct (Y/N).

 ${\bf o}$ Identification of the junction of the cystic duct with the common bile duct (Y/N).

- **o** Identification of the junction of the cystic duct with the gall bladder (Y/N).
- **o** Identification of the common hepatic duct (Y/N).
- o Identification of anatomical variables (yes/no).

- Identification of biliary structures after dissection of the hepatocystic triangle.

o Identification of cystic duct (yes/no).
o Identification of common bile duct (Y/N).
o Identification of the junction of the cystic duct with the common bile duct (Y/N).

o Identification of the junction of the cystic duct with the gall bladder (yes/no).

o Identification of the common hepatic duct (Y/N).

o Identification of anatomical variables (yes/no.).

- Degree of identification of biliary structures prior to dissection of the hepatocystic triangle
 - 1=slightly 2=sufficient 3=quite a lot 4=good 5=excellent
- Degree of identification of biliary structures after dissection of the hepatocystic triangle:
 - 1=slightly 2=sufficient 3=quite a lot 4=good 5=excellent
- Extent to which fluorescence cholangiography was perceived to be useful for surgery
 - Not useful Moderately useful Very useful
- Extent to which the fluorescence of the liver background (contrast between liver and ducts) was perceived as disturbing.

0=absence of disturbance 1=slightly disturbed 2=disturbed visualisation, but cystic-choledochal junction was clearly visible before dissection 3= visualisation disturbed and the cystic-choledochal junction was visible only after dissection 4= very disturbed: it was impossible to visualise the biliary structures correctly.

3. Secondary objectives.

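### The main objective asks about dose and about timing, but the SAP names only a four-group comparison with no dose, time or interaction contrast, and the stated power of .95 fits a 1-df contrast rather than that comparison

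*SAP*

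**What the plan says.** The working hypothesis (SAP section 1) is that visualisation differs "as a function of drug dose and time of administration". The main objective (Protocol section 8, SAP section 2) names both doses and intervals. Protocol section 12 explains the design: "The reason for the existence of 4 comparative groups is to study the efficacy of different dosage and interval of administration of the IV". The groups in Protocol section 18 fully cross fixed and weight-adjusted dosing with early and immediate administration.

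The analysis of the main objective in SAP section 2 is a single instruction: "Carry out a comparative analysis between the different groups (G1/G2/G3/G4) and the following qualitative variables". Sixteen variables follow: six yes/no items before dissection, the same six after it, and four graded scales (two of 1–5, one of three levels, one of 0–4). No test, contrast or model is named. SAP section 1 adds: "The primary endpoints are dichotomous and polytomous qualitative variables".

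Protocol section 21 supplies the methods. For dependence between categorical variables, "contingency tables will be used with Pearson's Chi-square test, Fisher's exact test, McNemar's test" or Cochran's Q. Beyond that, "A category comparison study could also be done using odds ratios between categories of clinical interest". Logistic regression appears only as an optional classification tool, and the closing note of the SAP leaves that part unsettled.

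The sample-size paragraph of the same section begins "Since the main objective is to analyse whether there are differences between the doses and administration times of the 4 treatment groups" and says that the effect of n=200 "on the statistical contrasts in this type of variables is $w=0.25$ with a power.95" at alpha 0.05. It gives no degrees of freedom.

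**The concern.** A four-group test that rejects shows only that the regimens are not all alike. Whether dose, timing or their combination is responsible needs a further comparison, and none is prespecified. The trial could therefore finish with a significant result and no planned answer to its own question. Contrasts chosen after the results are seen would carry less weight, particularly in an open-label trial whose outcomes are judged by surgeons and whose subjectivity the protocol acknowledges in section 30.

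Two related points depend on which analysis is meant. Power falls as degrees of freedom rise at a fixed w, so a figure without df cannot be matched to a test. And if the graded scales are analysed as unordered categories, power is lost whenever an effect moves the scale in one direction.

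**Working it through.** **1. The plan's power figure.** Inputs from Protocol section 21: n=200, w=0.25, alpha=0.05. The noncentrality is λ = n·w² = 200 × 0.0625 = 12.5. Power is the probability that a noncentral chi-square with that λ exceeds the central chi-square critical value. With four groups, df = (4−1)(k−1) for k outcome levels.

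| Comparison | df | Critical value | Power at n=200 | n for .95 at w=0.25 |
|---|---|---|---|---|
| Two-level factor by yes/no item | 1 | 3.84 | 0.942 | 208 |
| Four groups by yes/no item | 3 | 7.81 | 0.856 | 275 |
| Four groups by three-level scale | 6 | 12.59 | 0.758 | 334 |
| Four groups by five-level scale | 12 | 21.03 | 0.623 | 414 |

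The stated .95 is approximately reproduced only at 1 df. At alpha 0.025 the 1-df power is 0.902.

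These figures hold w fixed. Pooling over the other factor keeps w only if a single factor acts. With assumed group rates of 60/70/70/80% (mean 70%), the four-group w is √[((0.10² + 0 + 0 + 0.10²)/4)/(0.7 × 0.3)] = 0.154. The pooled 65 v 75% comparison has w = √[0.05²/(0.7 × 0.3)] = 0.109.

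**2. What contrasts would gain or lose on a yes/no item.** The documents give no event rates, so all rates below are assumptions. Simulation: 40,000 trials of 4 × 50, Pearson test on the 4×2 table at 0.05 against Wald tests of effect-coded dose and time terms at 0.025 each.

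| Assumed pattern | Four-group test | Contrast |
|---|---|---|
| Timing only, 60 v 80% | about 75% | time 81% |
| Both factors, 60/70/70/80% | 42% | 24% per factor; 43% at least one |
| One regimen better, 60/60/60/85% | 83% | 44% per factor; about 68% at least one |
| Crossed, 60/80/80/60% | 75% | about 2% per factor; interaction 88% at 0.05 |

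Per factor, the four-group test does better in three of the four patterns. The argument for the contrasts is that they answer the stated question, not that they always have more power. Interaction power in the one-regimen pattern is 56% at 0.05.

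**3. Order on the five-level scales.** Assumed timing-only shift with odds ratio 2.2 and three assumed baseline distributions, 4 × 50: unordered 4×5 table 36–48%; Kruskal–Wallis 64–74%; proportional-odds time term at 0.025, 71–82%. For an assumed change in spread by timing (10/15/30/30/15% v 22/13/13/22/30%) the order reverses: unordered 81%, Kruskal–Wallis 7%, proportional-odds time term 9% at 0.05.

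**4. Confidence level against test level.** If each contrast is tested at 0.025 but reported with a 95% interval, the interval can exclude an odds ratio of 1 while the test is not significant. In the simulations of step 2 this happened per factor in about 10% of trials for 60/70/70/80%, 12% for 60/60/60/85%, and 7% for timing at 60 v 80%.

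**The case against.** The best defence is that dose-by-outcome and time-by-outcome tables were intended all along. Protocol section 14 records dose type and interval as separate two-level fields, section 21 speaks of contrasts between doses and administration times, and 1 df is where the .95 nearly reproduces. That is plausible, and it is why the power figure should not be called wrong in itself. A reader might infer that the trial is undersized or that the sponsor miscalculated. The documents do not support this, because no df is stated and the figure fits a 1-df contrast. The defence does not close the gap, since SAP section 2 names only the four-group comparison.

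A second defence is that the trial compares four regimens; neither document calls it factorial. Under that reading too, no pairwise or follow-up comparison is stated.

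A reader might also infer that the plan prescribes only unordered tests for the graded scales. That is too firm. The SAP names no test, and Protocol section 21 says the tools will depend on the nature of the variables. Unordered testing is a likely inference from the SAP's classification of the endpoints and the protocol's list. Nor is an ordered test always better, as the change-in-spread example shows.

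Finally, replacing the four-group test with the contrasts would be a trade-off, not a clear gain. That objection stands, and the fix keeps the four-group test.

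**Conclusion.** The gap holds: the hypothesis and main objective ask about dose and about timing, and no prespecified analysis would attribute a four-group difference to either. The data can answer the question; the plan does not say how.

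The .95 does not belong to the only comparison the SAP names. At w=0.25 the shortfall from .95 is about 9 points for the yes/no items (0.950 − 0.856), 19 for the three-level scale (0.950 − 0.758) and 33 for the five-level scales (0.950 − 0.623). These figures rest only on the protocol's n, w and alpha and on the dimensions of the tables. All simulated powers rest on assumed rates and distributions, and show direction rather than expected values for this trial. The point on the graded scales is a missing test specification with a probable consequence. The SAP should be changed on all three counts.

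**What to change.** 1. Keep the four-group comparison. For each primary variable add prespecified dose, time and dose × time interaction contrasts, from a logistic model (yes/no) or a proportional-odds model (graded). Report odds ratios beside the four regimen rates or level distributions. State which analysis is primary. Match interval to test: 97.5% intervals if each contrast is tested at 0.025, or 95% intervals labelled unadjusted. Do not call the contrasts confirmatory across the 16 primary variables without a multiplicity rule; a split within one variable does not supply one.
2. For the graded scales add an order-using test (Kruskal–Wallis or proportional odds) and always show the full level distributions. Note that such tests gain power for a one-directional shift but can miss a change in spread. Proportional odds is not assured on the liver-background scale, where levels 2 and 3 depend on when the junction became visible.
3. Restate the power in Protocol section 21 with the df and alpha of the test chosen: about 0.94 for a 1-df contrast at 0.05 (0.90 at 0.025), or 0.86, 0.76 and 0.62 for four-group tables with two, three and five levels, all at w=0.25.

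The cost is wording and some extra analysis. Dose type, interval and weight are already collected (Protocol section 14), and no added patients are needed. The downsides are more tests, limited interaction power, and main effects that mislead if the interaction is strong. The dose contrast compares two dosing rules: 0.05 mg/kg equals 2.5 mg at 50 kg (2.5/0.05) and 4.0 mg at 80 kg (80 × 0.05), so its size depends on the weight mix of the patients.

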- 4- **Postoperative control visit.** This will take place 30 days after the surgical intervention through the General and Digestive System Surgery Outpatient Department.

There is no treatment period as it is considered a diagnostic method. This period shall include intraoperative time.

A computerised block randomisation will be performed through CDRe. Participants will be assigned to each of the 4 treatment groups by non-stratified 1:1:1:1 randomisation.

As it is an intervention without a control group, blinding will not be performed in the trial. The end-of-study criterion will be completion of the follow-up period at the end of the trial. 30 days from the last patient included in the study.

19. Effectiveness Assessment

The following efficacy parameters shall be used:

- Degree identification of biliary structures prior to dissection of the hepatocystic triangle (1=poor, 2=sufficient, 3=sufficient, 4=good, 5=excellent).
- Degree of identification of biliary structures after dissection of the hepatocystic triangle (1=poor, 2=sufficient, 3=sufficient, 4=good, 5=excellent).
- Degree to which FC was perceived as useful for surgery (0=not useful, 1=moderately useful, 2=very useful).
- Degree to which the fluorescence of the liver background (contrast between liver and ducts) was perceived as disturbed (0=absence of disturbance, 1=slightly disturbed, 2=disturbed visualisation, but cystic-choledochal junction was clearly visible before dissection, 3=disturbed visualisation and cystic-choledochal junction was only visible after dissection, 4=very disturbed: it was impossible to visualise the biliary structures correctly).

20. Security Assessment

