In these secondary objectives, we tried to analyse predictors of the quality of the fluorescence technique. To this end, we have found numerous factors in the literature that could influence cholangiography. We want to show whether there are differences between the factors listed below and the different working groups.

a) To analyse the influence of body mass index on FC outcomes during CL.

In this section, we could recode the qualitative variable BMI into the different BMI subgroups defined by the World Health Organisation or use normal weight/overweight as the cut-off point.

Clasificación	IMC (Kg/m ²
Normal	18.5 - 24.9
Sobrepeso	25 - 29.9
Obesidad grado I	30 - 34.9
Obesidad grado II	35 - 39.9
Obesidad grado III	Más de 40

We could also analyse it as a quantitative variable and see if there is a correlation between them.

b) To analyse the influence of the type of biliary pathology requiring surgery and previous liver disease on the results of FC during LC.

Analyse whether there are differences between "Previous liver disease (NO/SI). In the SI group, break down the variables: fatty liver disease, hepatitis, liver cirrhosis". And the main variables shown.

c) To analyse the influence of the type of surgery (elective/early/ delayed surgery) on the results of FC during LC.

To analyse whether there are differences between the variables "type of surgery" and "indication for surgery".

d) To analyse the influence of previous gallbladder or bile duct instrumentation on the results of FC during LC.

To analyse whether there are differences between the variables "previous biliary explorations", "previous biliary prostheses" and "previous gallbladder drainage". Both separately and united in a single variable.

e) To analyse the influence of different laparoscopic imaging systems on the results of FC during LC.

To analyse whether there are differences between the variable "image system" and the main target variables.

f) To analyse the rate of intraoperative complications related to CF during LC.

To analyse intraoperative complication rates in the series.

g) To analyse the rate of postoperative complications related to CF during LC.

To analyse the postoperative complication rate for the series overall and for each type of Clavien-Dindo classification (consecutive variable).

Also to analyse separately the rate of bile duct injury and the characteristics of bile duct injuries (consecutive variables).

Analyse in-hospital and 30-day mortality rates.

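### The main G1–G4 comparison is unadjusted under non-stratified randomisation, although baseline factors that the SAP says could influence the image are already collected; prespecified adjustment is a cheap improvement of uncertain size

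*SAP*

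**What the plan says.** - **Main analysis (SAP section 2).** The instruction is to "Carry out a comparative analysis between the different groups (G1/G2/G3/G4) and the following qualitative variables". Sixteen variables follow: six yes/no items before dissection, the same six after it, and four graded scales. No covariate is mentioned.
- **Tests (Protocol section 21).** For categorical data, "contingency tables will be used with Pearson's Chi-square test, Fisher's exact test, McNemar's test" or Cochran's Q, with odds ratios as a possible addition. Logistic regression appears only as an optional classification tool, and the closing note of the SAP leaves even that open.
- **Allocation (Protocol section 18).** "Participants will be assigned to each of the 4 treatment groups by non-stratified 1:1:1:1 randomisation". Blocks are used, but no factor is balanced by design.
- **Prognostic factors (SAP section 3).** "we have found numerous factors in the literature that could influence cholangiography". BMI, biliary pathology and liver disease, type of surgery, previous instrumentation and imaging system each become a separate secondary objective; item a), for example, is "To analyse the influence of body mass index on FC outcomes during CL".
- **Data.** Protocol section 14 records these factors in the electronic CRF. SAP section 1 lists them among 16 baseline variables to be compared across groups to show homogeneity, and gives no step to take if they differ.
- **Size.** Protocol section 21: "possible losses of patients, we estimate a sample size of 200 patients"; the detectable effect "in this type of variables is $w=0.25$ with a power.95"; and "the contrasts will be performed at a significance level of 5" per cent.

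**The concern.** A covariate that predicts the outcome and is fixed before dosing can be put in the group model. This removes explained variation from the comparison and corrects for whatever imbalance the randomisation happens to leave. Here the investigators have named candidate factors, have the data, and do not stratify on any of them. The plan nevertheless leaves them out of the one comparison for which the trial was randomised.

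Two things are at stake. One is some power and precision. The other is how an uneven baseline table will be handled. The homogeneity check has no defined consequence, so a decision to adjust would be taken after the data are seen, across 16 outcomes, in an open trial with subjective grading.

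**Working it through.** **1. The plan's own figure.** Protocol section 21 gives n = 200, w = 0.25, alpha = 0.05 and power 0.95. The noncentrality is λ = n·w² = 200 × 0.0625 = 12.5. Noncentral chi-square power is 0.942 with 1 df and 0.856 with 3 df. The stated figure therefore reproduces only for a 1-df contrast. Four groups by a yes/no item has 3 df, so 0.856 is the baseline for what follows. That shortfall is a separate matter.

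**2. Approximate value of adjustment.** The documents give no R² for the baseline factors, so R² is assumed. Effective N = 200/(1 − R²).

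| Assumed R² | Effective N | 3-df power |
|---|---|---|
| 0 | 200 | 0.856 |
| 0.05 | 211 | 0.875 |
| 0.10 | 222 | 0.894 |
| 0.20 | 250 | 0.928 |
| 0.30 | 286 | 0.958 |

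**3. Simulation of the four-group comparison.** Assumptions: 50 per group, group rates set to give w = 0.25, and 2,000 trials per setting. There are three covariates: one continuous, one present in 30% and one in 20%. Their odds ratios are 0.67/0.55/0.67 (weak), 0.50/0.35/0.50 (moderate) and 0.37/0.22/0.37 (strong). Unadjusted Pearson chi-square is compared with the adjusted 3-df likelihood-ratio test.

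| Overall identification | Covariates | Unadjusted power | Adjusted power | SD of G4−G1 risk difference, unadjusted / standardised |
|---|---|---|---|---|
| 70% | no effect | 0.877 | 0.884 | 0.087 / 0.088 |
| 70% | weak | 0.864 | 0.890 | 0.087 / 0.086 |
| 70% | moderate | 0.878 | 0.931 | 0.084 / 0.078 |
| 70% | strong | 0.880 | 0.950 | 0.086 / 0.077 |
| 85% | no effect | 0.896 | 0.918 | 0.068 / 0.069 |
| 85% | weak | 0.893 | 0.923 | 0.067 / 0.066 |
| 85% | moderate | 0.900 | 0.946 | 0.068 / 0.065 |
| 85% | strong | 0.902 | 0.959 | 0.066 / 0.061 |

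The no-effect rows matter. At 85% the adjusted test appears to gain 0.918 − 0.896 = 2.2 points from covariates that do nothing. That is the liberality of the likelihood-ratio test, and it accounts for most of the 3.0 points in the weak row. The SD column is free of this problem. At 70% with strong covariates the variance ratio is (0.086/0.077)² = 1.25, so adjustment is worth about 25% more patients. With weak covariates it is (0.087/0.086)² = 1.02.

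Two further sets of 3-df runs with five covariates gave 65% to 68% and 67% to 71% (weak), and 48% to 58% and 55% to 68% (strong). The largest gain in each of the three simulation sets is thus 7, 10 and 13 points.

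**4. Type I error.** The adjusted likelihood-ratio test ran at 5.1–6.7% in the runs tabulated above. With five covariates it ran at about 5.5–7.4%, against 4–7% for Pearson.

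**5. Chance imbalance.** For a factor present in an assumed 25%, counts per group are Binomial(50, 0.25). The highest and lowest of four groups differ by at least 8 patients (16 points) with probability 0.304. For the pooled timing contrast, 100 against 100, a 16-point gap has probability of only about 1%.

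To turn a 16-point gap into an outcome shift, take 70% identification without the factor (odds 2.333). With OR 0.5 the rate becomes 1.167/2.167 = 0.538, a shift of 0.162 × 0.16 = 2.6 points. With OR 0.2 it becomes 0.467/1.467 = 0.318, a shift of 0.382 × 0.16 = 6.1 points. The SE of a 50 against 50 difference at 70% is √(2 × 0.7 × 0.3/50) = 0.092, or 9.2 points.

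**6. The homogeneity check.** If the 16 baseline tests were independent at 5%, at least one would be significant with probability 1 − 0.95¹⁶ = 0.56 under correct randomisation. The check cannot stand in for a prespecified adjustment.

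**The case against.** The strongest reply is that nothing here is an error. Randomisation makes the unadjusted test valid, and its 5% level already covers chance case mix. That stands. A reader might infer that the planned comparison is biased, or that imbalance will often pass for a dose or timing effect. The documents do not support this: the shifts in step 5 are smaller than one standard error, and the 30% imbalance figure belongs to the extremes of four groups, not to the timing contrast.

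The gain also rests wholly on assumed covariate strength. The SAP says only that the factors could influence cholangiography. With weak factors there is little to win. That stands.

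Nor is adjustment free. A simulated 1-df timing test held 4.8% type I error with and without covariates, but this does not carry over to the four-group test. In null runs with five covariates, the likelihood-ratio test reached 7.3% at about 92% identification and 9.5% at about 96%; most of the excess was present without covariates too (5.4–8.9%). At an assumed 92%, 200 × 0.08 = 16 *no* results would have to support three group terms plus five covariates. A fixed five-covariate model for all 16 outcomes is therefore too rigid. That stands.

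The choice of covariates can be questioned as well. Previous acute cholecystitis is not among the factors in SAP section 3, although Protocol section 8 names previous inflammatory changes. Imaging system is in SAP section 3, but Protocol section 14 records it with the procedure, and the documents do not show that it is fixed before dosing.

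Finally, the SAP is not silent. Section 3 speaks of differences between the factors and the working groups, and the protocol permits logistic regression. Neither amounts to a prespecified adjusted group comparison.

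**Conclusion.** The point holds as a recommended, low-cost improvement, not as a flaw that invalidates the main analysis. The documents plan no adjusted G1–G4 estimate, either primary or supportive, under non-stratified allocation and with the relevant baseline data in hand.

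The loss is in power, precision on the rate scale and protection from chance imbalance. Over the assumed range it is about 2 to 4 power points if the factors are weak and up to about 7 to 13 if they are strong. Part of this reflects the liberal likelihood-ratio test, and nothing real is gained if the factors have no effect.

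The absence of a rule for uneven baselines is certain from the text and does not depend on those assumptions.

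**What to change.** In SAP section 2, before any results are seen:

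- For each yes/no item, prespecify a logistic model with the randomised group terms and a short list of pre-dose covariates, for example BMI (continuous), type of surgery (elective against early/deferred) and previous liver disease. Type of surgery qualifies because it follows from the indication at inclusion.
- Add previous acute cholecystitis and previous biliary instrumentation only where the number of *no* results supports them, by a stated rule.
- For each graded item, prespecify an ordinal logistic model with the same terms, and check proportional odds.
- Report standardised risk differences with 95% confidence intervals for yes/no items. The adjusted odds ratio is conditional, so the precision gain appears on the rate scale.
- For near-ceiling items, use Firth-penalised likelihood or fewer covariates. More generally, use a small-sample or penalised test, because the plain likelihood-ratio test runs above 5%.
- For the two anatomical-variant items, use the unadjusted table alone, since no gain is expected.
- Keep the unadjusted contingency tables alongside throughout.

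The cost is SAP text and some R code, with no new data, visits or patients. The real downsides are the extra modelling checks and the need to confirm type I error for the chosen method.
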